### 8. ASSESSMENT OF SAFETY

### 8.1 Specification of Safety Parameters

- Post-treatment skin responses, side effects (e.g., erythema, edema) will be scored by the study investigators, as appropriate, using a scale of 0 to 3 (none to marked), immediately after treatment, for each treatment.
- Side effects (prolonged erythema, edema, skin darkening or lightening in the treatment area, scarring, dryness/flakiness, blistering) will be scored, using a scale of 0 to 3 (none to marked), by study investigators at the beginning of every subsequent treatment, and at all follow-up visits.
- Subject's will log post-treatment skin responses, side effects (e.g., erythema, edema) using a scale of 0 to 3 (none to marked), after each treatment for seven (7) days in the patient diary.
- In addition, study subjects will be instructed to report all complications experienced post study procedure to the site personnel as soon as they occur/are observed.
- It is the Investigator's responsibility to determine seriousness, severity, and relatedness of the Adverse Event to the device and the procedure using the definitions below.

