### 4.2.3 Safety Endpoints

Serious Adverse Events (SAEs) related and unrelated to the treatment procedure or to the CLEAR + BRILLIANT TOUCH® diode laser.

The severity of post-treatment skin responses:

- Immediate post-treatment erythema and edema (Visits: 1 and or 2 if screening and treatment on same day, Visits 3, 4 and 5)
- Prolonged post-treatment erythema, edema, dryness/flakiness, hypopigmentation, hyperpigmentation, blistering, scarring. (Visits 6 & 7)

The evaluation of pain and discomfort immediately after the treatment (within 60 minutes) as reported by the subject on a visual analog scale (VAS).

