#### Visit 1 (Day 0-30)

Screening

A prospective subject is to be examined to determine if they qualify for entry into the study. This initial examination will include:

- Obtain written Informed Consent and photographic release
- Review Inclusion/Exclusion Criteria
- Record Medical History/Meds/Vital Signs
- Urine Pregnancy Test (if applicable): only one is necessary prior to start of treatments.
- Dispense CeraVe® Products
- Skin types IV-VI: Begin Hydroquinone 8% QHS at discretion of treating physician 2-3 weeks prior to first treatment. Hold while skin is healing, then restart QHS or as directed.
- Investigator Assessments: Glogau Photodamage, Fitzpatrick Skin Type and Wrinkle & Elastosis Scale
- Biopsy #1 of five patients (baseline)

Note: Screening and Baseline visits may occur on the same day for non biopsy patients.

#### Visit 2

Baseline/Treatment #1 (Screening/Baseline may be on same day)

This treatment visit will include:

- Photographs prior to treatment: wait at least 15 min indoors, 2D standard photography captured via Canfield VISIA CA.
- Urine Pregnancy Test (if applicable): only one is necessary prior to start of treatments.
- · Laser treatment to the face
- VAS Scale
- Post Treatment Skin effects (provider)
- Review for Adverse Events (provider)
- Subject Diary post treatment (7 days) given to patient.

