#### 8.1.2 Definition of Adverse Events (AE)

An adverse event (AE) is any untoward or unfavorable medical occurrence in a human subject, including any abnormal sign (for example, abnormal physical exam or laboratory finding), symptom or disease temporarily associated with the subject's participation in research whether or not considered related to the subject's participation in the research period.

A pre-existing condition (one that is present at the start of the study) will be recorded as an AE only if the frequency, intensity or the character of the condition worsens during the study period.

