#### **Statistical Analysis Plan Table**

Evaluation	Change from baseline	Notes/Interpretation
Investigator	The mean score (0-4) will	Significantly greater than 0
Quartile	be compared to the	indicates improvement.
Improvement	constant 0, using Wilcoxon	
Score	signed rank test	
SAEs	NA	Zero or low number of SAEs is
		favorable
Tolerability	NA	Lower score indicates better
parameters		tolerability
VAS	NA	Lower score indicates better
		tolerability
Biopsy parameters	NA	Descriptive statistics only
Individual	NA	A binomial test (sign test) P value
response data		will be provided. A higher
(GAIS and		percentage of combined favorable
satisfaction)		responses with a significant P
		value indicates positive subject
		perceptions of the test material.
Blinded	The mean score (0-4) will	Significantly greater than 0 indicates
Investigators	be compared to the	improvement.
	constant 0, using Wilcoxson	
	signed rank test	

All statistical tests will be 2-sided at significance level alpha=0.05 unless specified otherwise. *P* values will be reported to 3 decimal places (0.000).

No multiple testing corrections will be considered in the study. Statistical analyses are performed using SAS software version 9.4 (SAS Statistical Institute). The statistical results will be sent to the Sponsor along with raw data in a Microsoft Excel document at completion of the study.

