# **Appendix Section**

## Appendix A: Glogau Photodamage Scale

Glogau Photodamage Scale					
Group Classification	Typical Age	Description	Skin Characteristics		
I Mild	28-35	No Wrinkles	Early Photoaging: mild pigment changes, no keratosis, minimal wrinkles, minimal or no makeup		
II Moderate	35-50	Wrinkles in motion	Early to Moderate Photoaging: Early brown spots visible, keratosis palpable but not visible, parallel smile lines begin to appear, wears some foundation		
III Advanced	50-65	Wrinkes at rest	Advanced Photoaging: Obvious discolorations, visible capillaries (telangiectasias), visible keratosis, wears heavier foundation always		
IV Severe	60-75	Only wrinkles	Severe Photoaging; Yellow-gray skin color, prior skin malignancies, wrinkles throughout-no normal skin, cannot wear makeup because it cakes and cracks		

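### No 0-3 skin-response score is planned before Treatment #1, so the raw tolerability rates can mix pre-existing findings with laser effects

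*Combined protocol and SAP*

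**What the plan says.** Section 8.1 sets two investigator scoring times. Immediate responses are graded "using a scale of 0 to 3 (none to marked), immediately after treatment, for each treatment". Prolonged side effects are graded "by study investigators at the beginning of every subsequent treatment, and at all follow-up visits". The subject diary also starts only after each treatment.

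Section 4.2.3 makes these grades a safety endpoint: "Prolonged post-treatment erythema, edema, dryness/flakiness, hypopigmentation, hyperpigmentation, blistering, scarring. (Visits 6 & 7". That is seven items.

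In Section 6.8, the schedule marks a side-effects evaluation at Visit 2 without saying whether it comes before or after the laser. The Visit 2 list names it "Post Treatment Skin effects (provider" and places it after the laser treatment. The gradings at screening are "Investigator Assessments: Glogau Photodamage, Fitzpatrick Skin Type and Wrinkle & Elastosis Scale".

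Section 10.2.1 summarises tolerability parameters by N, mean, median, SD, minimum and maximum, and by counts and percentages. The SAP table enters NA under change from baseline for tolerability, with the note "Lower score indicates better" tolerability. Section 4.1 states that there is no control group.

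The rule on pre-existing conditions is in Section 8.1.2. Such a condition "will be recorded as an AE only if the frequency, intensity or the character of the condition worsens during the study period". That rule governs AE recording; no equivalent is written for the 0-3 grades.

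**The concern.** The study enrols people because their skin is already photodamaged. Under Appendix A, even the mildest eligible Glogau group has some pigment change, and Group II is described with "Early brown spots visible". Appendix B lists dyschromia in class II, which is also eligible. Hyperpigmentation and hypopigmentation are then safety endpoints on a none-to-marked scale.

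The protocol also creates some findings before any laser exposure. Up to five subjects have a punch biopsy at screening in the treatment area (6.5.2), and Section 9.2.3 warns of a possibly permanent scar; scarring is a scored item. Subjects with skin types IV-VI may start hydroquinone in the weeks before Treatment #1 (6.2), so their pigment may already be changing when laser treatment begins.

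Without a pre-laser grade, a count of subjects at grade 1 or more at Visits 6 and 7 has two possible meanings: all findings present, or only findings that the investigator judged new. Section 8.5 allows termination or modification to be recommended when a safety component occurs more often than anticipated, so the meaning of the rate matters beyond the final report.

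**Working it through.** The plan gives no figure on this point to reproduce. The check is a comparison of the scoring times, followed by an illustration with assumed inputs.

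**Is there any grade before Treatment #1?**

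- Section 8.1, immediate responses: after each treatment. No.
- Section 8.1, prolonged effects: at each subsequent treatment and at follow-up. Treatment #1 is not a subsequent treatment. No.
- Section 4.2.3: prolonged items at Visits 6 and 7. No.
- Section 6.5: immediately after treatment and at follow-up. No.
- Section 6.8, Visit 2 list: one provider assessment, post-treatment. No.
- Section 6.8, Visit 1 list: Glogau, skin type, wrinkle and elastosis. None is an item-level grade of erythema, pigment, dryness or scarring.

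**Does the analysis supply the comparison?** Section 7.2 ties the efficacy score to the baseline photographs. No section does the same for the 0-3 safety grades, and Section 10.2.1 summarises the grades themselves.

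**Illustration.** Inputs: N = 30 (the enrolment ceiling in Sections 4.1 and 5.2); p0 = share of subjects already at grade 1 or more (assumed); q = probability of a laser effect, independent of p0 (assumed). Subjects are taken to be graded as seen, and pre-existing findings to persist.

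- Expected number counted with no laser effect (q = 0): N × p0.
- Chance of at least one such subject: 1 − (1 − p0)^30.

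| Assumed p0 | Expected number of 30 | Chance of at least one |
|---|---|---|
| 5% | 1.5 | 0.785 |
| 10% | 3 | 0.958 |
| 20% | 6 | 0.999 |
| 30% | 9 | about 1.0 |

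Adding a laser effect with p0 = 20% and q = 5%:

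- Raw rate: 1 − (1 − 0.20)(1 − 0.05) = 1 − 0.76 = 24%, or 30 × 0.24 = 7.2 subjects.
- New findings in previously clear skin: 30 × 0.80 × 0.05 = 1.2 subjects, or 4% of 30.

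In this example the raw rate is six times the rate of new findings in clear skin (24% against 4%). The ratio follows from the assumed p0 and q and is not a forecast.

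**The case against.** The best reply is that the items are worded as treatment effects. Prolonged erythema and skin darkening or lightening describe change after exposure, so a brown spot present at entry is not a side effect and should be graded 0. Many investigators would score that way. This stands as a reasonable reading, but it is not written down, the scale is a level running from none to marked, and hyperpigmentation and scarring in Section 4.2.3 can be read as states. The scoring convention is left to an unblinded rater.

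A reader might infer that pre-existing findings cannot be told apart from laser effects at all. The documents do not support that. Standardised photographs are taken before Treatment #1 (6.8), so pigment, redness and scars can be checked subject by subject. Medical history and Glogau grade are recorded. Section 5.4 excludes melasma, rosacea, eczema, psoriasis, rashes, keloid predisposition, recent sunburn and skin still recovering from a cosmetic procedure, which weakens the case for baseline redness and dryness in particular. It does not exclude ordinary photoaging pigment or every old scar.

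Nor does the NA in the SAP table prove that the grades are absolute levels. That column holds the tests against zero, and GAIS is also NA although Section 7.6 defines it against a baseline photograph.

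The AE route does separate old from new through its worsening rule, with severity and relatedness recorded. What remains open is the scored tolerability endpoint, which is descriptive with no formal test or numerical stopping threshold.

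**Conclusion.** The point holds in a limited form. No 0-3 grade is planned before Treatment #1, and the tolerability summary has no stated comparison with the subject's own pre-treatment skin. In an uncontrolled study the reported rates can therefore mix old and new findings, or rest on informal discounting. Pigment change is the main item affected, followed by scarring in the biopsy subjects. The evidence for erythema and dryness is weaker.

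The size is unknown. The figure of about 3 in 30 rests on an assumed 10% starting at grade 1 or more and on grading as seen; if every rater already scores only change, the excess is zero. A reader might argue that, because Appendix A gives every eligible subject some pigment change, the hyperpigmentation rate could read anywhere from 0% to 100%. That is only the logical range, and the documents do not say that entry pigment is to be scored as harm.

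This is a gap in one safety summary. It does not affect the primary effectiveness endpoint, and it is cheap to close.

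**What to change.** - At Visit 2, before anesthetic and laser, have the investigator grade the same seven items 0-3 on the same form.
- In Section 10.2.1 and the SAP table, define new or worsened as a post-baseline grade above the subject's own pre-treatment grade. Report its counts and percentages beside the raw grades.
- In the schedule, state that the Visit 2 side-effects evaluation has both a pre-treatment and a post-treatment score.
- For subjects already treated, grade pigment, erythema and scarring from the Visit 2 photographs, and note that dryness cannot be recovered reliably.

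The cost is one short form at a visit already held, the SAP wording, and some rater time for retrospective photo grading if enrolment has begun.

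One limit should be stated in the report. A pre-laser grade captures the first biopsy scar and the pigment state at Visit 2, but not a scar from the day-14 biopsy or later hydroquinone use.

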#### 8.1.1 Definition of Serious Adverse Events (SAE)

### Serious Adverse Event (SAE) is an adverse event that:

- Led to a death or
- Led to a serious deterioration in the health of a subject that:
  - Resulted in a life-threatening illness or injury,
  - Resulted in a permanent impairment of a body structure or body function,
  - Required inpatient hospitalization or prolongation of existing hospitalization,
  - Resulted in medical or surgical intervention to prevent impairment to body structure or a body function, or
  - Lead to fetal distress, fetal death or congenital abnormality or birth defect.

All SAEs that occur during the study period, whether considered to be related to the study device or not, must be reported to the Sponsor within 24 hours of knowledge of the event. IRB reporting requirements may also apply to SAEs.

#### 8.1.2 Definition of Adverse Events (AE)

An adverse event (AE) is any untoward or unfavorable medical occurrence in a human subject, including any abnormal sign (for example, abnormal physical exam or laboratory finding), symptom or disease temporarily associated with the subject's participation in research whether or not considered related to the subject's participation in the research period.

A pre-existing condition (one that is present at the start of the study) will be recorded as an AE only if the frequency, intensity or the character of the condition worsens during the study period.

#### 8.1.3 Definition of Unanticipated Adverse Device Effect (UADEs)

Any serious adverse effect on health or safety or any life-threatening problem or death caused by, or associated with, a device, if that effect, problem, or death, was not previously identified in a nature, severity, or degree of incidence in the investigational plan or application (including a supplementary plan or application), or any other unanticipated serious problem associated with a device that relates to the rights, safety, or welfare of subjects

In addition, any UADEs will be reported to the Sponsor and the reviewing IRB as soon as possible, but no later than within 24 hours of knowledge of the event.

All adverse events, anticipated or unanticipated, will be monitored until they are adequately resolved or explained.

#### 8.1.4 Definition of Device Malfunction

Malfunction means the failure of a device to meet its performance specifications or otherwise perform as intended. Performance specifications include all claims made in the labeling for the device. The intended performance of a device refers to the intended use for which the device is labeled or marketed, as defined in 21 CFR § 801.4.

### 8.2 Adverse Event / Device Malfunction Reporting

In the case of an AE (Serious and Significant Non-Serious) or UADE the Investigator must:

Report the AE or UADE to the Medical Monitor within 24 hours of knowledge of the event using the Sponsor-provided form (SAE/UADE reporting form, Appendix D) by emailing the completed form to the Medical Monitor

The Medical Monitor will email/fax a copy of the form immediately (within 24 hours) for SAEs/UADEs only to upon receipt.

In the case of Device Malfunctions, the Investigator must:

Report the Device Malfunction within 24 hours using the Sponsor-provided form (Device Malfunction reporting form, Appendix E) by emailing the completed form to

All AEs observed by study subjects, Investigators or other study staff from first exposure to the study product through last study follow-up visit will be recorded. If a device-related AE, SAE, unanticipated serious device related effect or device malfunction is ongoing at the final study visit, the subject will be followed until resolution, until the condition stabilizes, until the event is otherwise explained, or the subject is lost to follow-up. The Investigator should make every effort to ensure the follow-up includes any supplemental investigations as may be indicated to elucidate, as completely practical, the nature and or causality of the AE or SAE. This may include unscheduled follow up visits for AE assessment.

Study subjects will be instructed to report all adverse events to the clinical study staff and information will be collected throughout the study and recorded on the case report forms and reported to Solta Medical Customer Service.

#### 8.3 Classification of Adverse Events

The severity of adverse events will be categorized using the following criteria:

- Mild: easily tolerated by the subject causing minimal discomfort and not interfering with everyday activities. These events generally do not require treatment.
- Moderate: sufficiently discomforting to interfere with normal everyday activities.
   These events are usually relieved by simple therapeutic measures.
- **Severe**: prevents normal everyday activities these events may require systemic drug therapy or other medical treatment.

### 8.4 Relationship to the study device and/or procedure

The causality assessment is a determination of the relationship between the investigational device or surgical procedure and the occurrence of an AE/SAE.

The possibility of a link between the study device or surgical procedure and an AE will take into consideration (as a minimum) the following criteria:

- Existence of a temporal link between the event and administration of the study device.
- Event is not explained by any other condition, measure or environmental factor.

For this study, causality will be defined as:

- Related: There is at least a reasonable possibility that the AE/SAE is related to
  the study device or surgical procedure. Reasonable possibility means that there
  is evidence to suggest a causal relationship or association between the study
  device and the AE. Also referred to as an ADE.
- **Unrelated:** There is little or no reasonable possibility that the AE/SAE is related to the study device or surgical procedure. This assessment implies that the AE/SAE has no evidence to suggest either a causal relationship or association to the study device or surgical procedure and more likely or certain an alternative etiology exists.

### 8.5 Termination of Study Rules for Safety

The Sponsor and/or Investigator may recommend termination or modification of the study if there is an occurrence of any device or treatment related Serious Adverse Event using the following clinical protocol definitions of Serious Adverse Event in section 8.1.1 of this protocol. In addition, termination, or modification may be recommended for any other perceived safety concern based on clinical judgment, including but not limited to a higher than anticipated rate for any component of the safety measures, device failures result resulting in Adverse Events or unexpected SAEs.

### 9. RISKS AND BENEFITS

### 9.1 Benefits

A possible benefit of using the CLEAR + BRILLIANT TOUCH® diode laser technology in a combination wavelength same session treatment, over a series of four treatments, is an enhanced improvement in the tone, texture, radiance, fine lines, pore size and overall appearance of the skin compared to no treatment at all.

#### 9.2 Risks

#### 9.2.1 Expected Responses

Clinical studies have shown that CLEAR + BRILLIANT diode laser treatments have a demonstrated safety profile. There is a very low incidence of side effects and complications associated with treatment. Risks and discomforts for subjects who participate in this study are the same as for subjects undergoing any dermatological laser treatment. Eye injury due to use of the laser system is a risk to the subject and the operator. Appropriate eye protection will be used to minimize that risk. Mild to moderate local pain is a typical reaction to laser treatments. Topical anesthetic will be applied prior to laser treatments. Eye injuries may result from numbing cream getting into the eyes. Eyes will be covered with protective eyewear during treatment and should remain closed during the treatment.

### Expected Responses:

- Erythema (Redness)
- Edema (Swelling)
- Itching/Dryness
- Increased Skin Sensitivity
- Pain or Discomfort
- · Pinpoint Bleeding/Petechia

### 9.2.2 Unexpected Responses

The following complications are very rare but may be associated with non-ablative laser treatments. This is not intended to be an all-inclusive list, nor a substitute for informed consent, which should be provided by every individual.

Complication	Description
Discoloration	The possibility of temporary and permanent skin color change is known to exist with any laser treatment. Post-inflammatory hypopigmentation and hyper-pigmentation are known complications of many laser treatments and may occur with CLEAR + BRILLIANT TOUCH® treatment. Following appropriate instructions for sun protection will lower the risk for pigmentation changes.
Infection	A risk of infection exists whenever the skin is wounded. The possibility for infection exists even with non-ablative fractional laser devices such as the CLEAR + BRILLIANT TOUCH® System. An infection should be treated appropriately with topical and/or systemic medications.
Prolonged Redness	Mild-moderate transient erythema is an expected response with any laser treatment. However, if erythema is severe or persists significantly longer than expected, re-treatment should be avoided until the condition resolves. Reaction may vary on a person-to-person basis.
Scarring	The possibility for scarring exists with any laser treatment, even with non-ablative laser devices such as CLEAR + BRILLIANT TOUCH® System. Local scarring may occur directly from laser exposure if treatment procedures are not followed properly, or from infection or physical irritation such as picking and rubbing.
Delayed Wound Healing/Skin Textural Changes	Following any laser treatment, re-epithelialization may not occur as expected due to an individual's physiology (i.e. poor wound healing ability, or post-treatment care). This may result in undesirable textural changes.
Temporary Bruising	Temporary bruising may develop over the treated areas and typically dissipates within several days.

